8.2.8. Hepatitis C Testing and Monitoring

Initial testing for HCV infection includes testing for antibodies to HCV.

- If anti-HCV is positive, a serum test for circulating HCV RNA is required.
- If HCV RNA test is negative, the participant is not excluded.
- If HCV RNA test is positive, the participant is excluded (see Section 5.2).

Participants who have had HCV infection and been successfully treated, defined as a sustained virologic response (HCV RNA by PCR negative for at least 24 weeks following treatment completion) are not excluded on the basis of HCV, as long as HCV RNA test is negative at screening.

If HCV RNA is detected during the study, the study drug will be discontinued (see Section 7), and the participant should receive appropriate follow-up medical care.

8.2.9. Hepatic Safety Monitoring

Close hepatic monitoring

The laboratory tests listed in Appendix 5, including ALT, AST, ALP, TBL, direct bilirubin, GGT, and CK, should be repeated within 48 to 72 hours to confirm the abnormality and to determine whether it is increasing or decreasing, if any of the conditions listed in this table occur.

If a participant has the following elevations:

ALT or AST ≥ 3 times ULN

ALP ≥ 2 times ULN

TBL ≥ 2 times ULN (except for patients with Gilbert's syndrome)

Abbreviations: ALP = alkaline phosphatase; ALT = alanine aminotransferase; AST = aspartate aminotransferase; TBL = total bilirubin level; ULN = upper limit of normal.

If the abnormality persists or worsens, clinical and laboratory monitoring, and evaluation for the possible causes of the abnormal liver tests should be initiated by the investigator in consultation with the sponsor's designated medical monitor. At a minimum, this evaluation should include a physical examination and a thorough medical history, including symptoms, recent illnesses (for example, heart failure, systemic infection, hypotension, or seizures), recent travel, history of concomitant medications (including over-the-counter), herbal and dietary supplements, history of alcohol drinking, and other substance abuse.

Initially, monitoring of symptoms and hepatic biochemical tests should be done at a frequency of 1 to 3 times weekly, based on the participant's clinical condition and hepatic biochemical tests. Subsequently, the frequency of monitoring may be lowered to once every 1 to 2 weeks, if the participant's clinical condition and lab results stabilize. Monitoring of ALT, AST, ALP, and TBL should continue until levels normalize or return to approximate baseline levels.

Comprehensive hepatic evaluation

A comprehensive evaluation should be performed to search for possible causes of liver injury, if 1 or more of the conditions listed in this table occur:

If a participant has the following elevations:

ALT or AST ≥ 3 times ULN with hepatic signs/symptoms^a, or
ALT or AST ≥ 5 times ULN

ALP ≥ 3 times ULN

TBL ≥ 2 times ULN (except for patients with Gilbert's syndrome)

Abbreviations: ALP = alkaline phosphatase; ALT = alanine aminotransferase; AST = aspartate aminotransferase; TBL = total bilirubin level; ULN = upper limit of normal.

^a **Hepatic signs/symptoms are severe fatigue, nausea, vomiting, right upper quadrant abdominal pain, fever, rash, and/or eosinophilia $>5\%$.**

At a minimum, this evaluation should include a physical examination and a thorough medical history, as outlined above, as well as

- tests for prothrombin time (PT-INR)
- tests for viral hepatitis A, B, C, and E, and
- tests for autoimmune hepatitis, and an abdominal imaging study (for example, ultrasound or CT scan).

Based on the participant's history and initial results, further testing should be considered in consultation with the sponsor's designated medical monitor, including tests for

- hepatitis D virus (HDV)
- cytomegalovirus (CMV)
- Epstein-Barr virus (EBV)
- acetaminophen levels
- acetaminophen protein adducts
- urine toxicology screen

- Wilson's disease
- blood alcohol levels
- urinary ethyl glucuronide, and
- serum phosphatidylethanol.

Based on the circumstances and the investigator's assessment of the participant's clinical condition, the investigator should consider referring the participant for a

- hepatologist/gastroenterologist consultation
- magnetic resonance cholangiopancreatography (MRCP)
- endoscopic retrograde cholangiopancreatography (ERCP)
- cardiac echocardiogram, or
- liver biopsy.

8.2.9.1. Additional Hepatic Data Collection in Participants Who Have Abnormal Liver Tests During the Study

Additional hepatic safety data collection (hepatic safety eCRF) should be performed for participants who meet 1 or more of the following conditions:

- Elevation of serum ALT to ≥ 5 times ULN on 2 or more consecutive blood tests
- Elevated TBL to ≥ 2 times ULN (except for cases of known Gilbert's syndrome)
- Elevation of serum ALP to ≥ 2 times ULN on 2 or more consecutive blood tests
- Hepatic event considered to be an SAE.
- Discontinuation of study drug due to a hepatic event (Section 7.1).

Note: The interval between the 2 consecutive blood tests should be at least 2 days.

8.2.10. Suicidal Ideation and Behavior Risk Monitoring

Participants should be monitored appropriately and observed closely for suicidal ideation and behavior or any other unusual changes in behavior, especially at the beginning and end of the course of intervention. Participants who have signs of suicidal ideation or behavior should be considered for discontinuation of study drug, following a risk assessment (see Section 7). See Section 8.3.1.1 for timing of AE collection relative to collection of the C-SSRS.

8.2.10.1. Columbia Suicide-Severity Rating Scale

The C-SSRS is a scale that captures the occurrence, severity, and frequency of suicidal ideation and behavior during the assessment period via a questionnaire. The scale was developed by the National Institute of Mental Health (NIMH) trial group (TASA) for the purpose of being counterpart to the Columbia Classification Algorithm of Suicide Assessment (C-CASA) categorization of suicidal events.

For this study, the C-SSRS is adapted for the assessment of the ideation and behavior categories only. The Intensity of Ideation and Lethality of Behavior sections are removed.

The C-SSRS data will be entered in the eCRF.

8.2.10.2. Depression Assessment with 16-Item Quick Inventory of Depressive Symptomatology–Self Report

The QIDS-SR16 is a self-administered, 16-item instrument intended to assess the existence and severity of symptoms of depression as listed in the American Psychiatric Association's Diagnostic and Statistical Manual of Mental Disorders, 5th Edition.¹⁹ A participant is asked to consider each statement as it relates to the way he or she has felt for the past 7 days. There is a 4-point scale for each item ranging from 0 to 3. The 16 items corresponding to 9 depression domains are summed to give a single score ranging from 0 to 27, with higher scores denoting greater symptom severity. The domains assessed by the instrument include

- 1) sad mood
- 2) concentration
- 3) self-criticism
- 4) suicidal ideation
- 5) interest
- 6) energy/fatigue
- 7) sleep disturbance (initial, middle, and late insomnia or hypersomnia)
- 8) decrease/increase in appetite/weight, and
- 9) psychomotor agitation/retardation.

The QIDS-SR16 data will be collected via a tablet device and/or a web-based collection system.

8.3. Adverse Events and Serious Adverse Events

Adverse events will be reported by the participant or, when appropriate, by a caregiver, surrogate, or the participant's legally authorized representative.

The investigator and any qualified designees are responsible for detecting, documenting, and recording events that meet the definition of an AE or SAE and remain responsible for following up AEs that are serious, considered related to the study intervention or study procedures, or that caused the participant to discontinue the study intervention or the study (see Section 7).

Pregnancy after maternal or paternal exposure to IP does not meet the definition of an AE. However, to fulfill regulatory requirements, any pregnancy should be reported using the SAE process described in Section 10.3.4, to collect data on the outcome for both mother and fetus. See also Section 8.3.5.

8.3.1. Time Period and Frequency for Collecting Adverse Event and Serious Adverse Event Information

All AEs will be collected from the time of the participant's signing of the ICF until the participant's last post-treatment follow-up visit.

Likewise, all SAEs will be collected from the signing of the ICF until the last post-treatment follow-up visit.

Adverse events that begin before the start of study intervention but after signing of the ICF will be recorded on the Adverse Event eCRF.

Although all AEs after signing the ICF are recorded by the site in the eCRF/electronic data entry tool, SAE reporting to the sponsor begins after the participant has signed the ICF and has received study drug. However, if an SAE occurs after signing the ICF but prior to receiving study drug, the SAE needs to be reported ONLY if the SAE is considered reasonably possibly related to study procedures.

All SAEs will be recorded and reported to the sponsor or the sponsor's designee immediately, and under no circumstance should this exceed 24 hours, as indicated in [Appendix 3](#), Section 10.3.4. The investigator will submit any updated SAE data to the sponsor within 24 hours of it being available.

Investigators are not obligated to actively seek AE or SAEs after the conclusion of study participation, that is, once the participants have discontinued and/or completed the study (the Participant Study Disposition eCRF has been completed). However, if the investigator learns of any SAE, including a death, at any time after a participant has been discharged from the study, and the investigator considers the event to be reasonably related to the study intervention or study participation, the investigator must promptly notify the sponsor.

8.3.1.1. Adverse Event Monitoring with a Systematic Questionnaire

Nonleading (spontaneous) AE collection should occur before the collection of the C-SSRS.

If a suicide-related event is discovered during the C-SSRS collection, but was not captured during the nonleading AE collection, sites should not change the AE form. However, if an AE is serious or leads to discontinuation, the AE should be included on the AE form. Also, the process for reporting SAEs should be followed.

8.3.2. Method of Detecting Adverse Events and Serious Adverse Events

The method of recording, evaluating, and assessing causality of AE and SAE and the procedures for completing and transmitting SAE reports are provided in [Appendix 3](#), Section 10.3.3 and Section 10.3.4.

Care will be taken not to introduce bias when detecting AEs and/or SAEs. Open-ended and nonleading verbal questioning of the participant is the preferred method to inquire about AE occurrences.

8.3.3. Follow-up of Adverse Events and Serious Adverse Events

After the initial AE or SAE report, the investigator is required to proactively follow each participant at subsequent visits/contacts. All SAEs as well as AESIs, as defined in Section 8.3.6, will be followed until resolution, stabilization, the event is otherwise explained, or the participant is lost to follow-up, as defined in Section 7.3. Further information on follow-up procedures is provided in Appendix 3, Section 10.3.3.

8.3.4. Regulatory Reporting Requirements for Serious Adverse Events

Prompt notification by the investigator to the sponsor of a SAE is essential so that legal obligations and ethical responsibilities towards the safety of participants and the safety of a study intervention under clinical investigation are met.

The sponsor has a legal responsibility to notify both the local regulatory authority and other regulatory agencies about the safety of a study intervention under clinical investigation. The sponsor will comply with country-specific regulatory requirements relating to safety reporting to the regulatory authority, IRB/ IEC, and investigators.

An investigator who receives an investigator safety report describing an SAE or other specific safety information (for example, summary or listing of SAEs) from the sponsor will review and then file it along with the IB and will notify the IRB/IEC, if appropriate according to local requirements.

8.3.5. Pregnancy

For female participants and female partners of male participants, details will be collected for all pregnancies occurring from after the start of study intervention and until 12 weeks after the last dose.

If a pregnancy is reported, the investigator should inform the sponsor within 24 hours of learning of the pregnancy and should follow the reporting procedures outlined in Appendix 4, Section 10.4.3.

Abnormal pregnancy outcomes (for example, spontaneous abortion, fetal death, stillbirth, congenital anomalies, ectopic pregnancy) are considered SAEs.

8.3.6. Adverse Events of Special Interest

Adverse events of special interest for this study include

- systemic allergic/hypersensitivity reactions, including CRS
- serious infections and opportunistic infections, and
- injection site reactions.

If such AESIs are reported, sites will be prompted to collect additional data as described in the following subsections.

8.3.6.1. Systemic Hypersensitivity Reactions

Many drugs, but particularly biologic agents, carry the risk of systemic hypersensitivity reactions. If such a reaction occurs, additional data describing each symptom should be provided to the sponsor in the eCRF.

Sites should have appropriately trained medical staff and appropriate medical equipment available when the study participants are receiving study drug. It is recommended that participants who experience a systemic hypersensitivity reaction be treated per national and international guidelines.

Blood sample collection for systemic allergic/hypersensitivity events, including cytokine release syndrome

In the case of generalized urticaria or anaphylaxis, additional samples as described in [Appendix 2](#), Section 10.2.2 should be collected. Laboratory results are provided to the sponsor via the central laboratory.

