 - The investigator, after consultation with the sponsor's designated medical monitor, determines that a systemic hypersensitivity reaction has occurred and is related to study drug administration.
 - The participant has any of the following results on 2 consecutive samples taken at least 48 hours, but no more than 1 week, apart:
 - Total WBC <1000 cells/μL
 - ANC <500 cells/μL
 - ALC <200 cells/μL
 - Hemoglobin <6.5 g/dL
 - The participant develops CRS. In consultation with the Lilly medical monitor, if an AE is deemed possibly or probably due to CRS based on the details and severity of clinical signs and symptoms, time course of symptom onset relative to study drug administration, and if possible, a cytokine panel from a blood sample obtained at the time of the event,

the participant will be discontinued from study treatment, and will continue safety follow-up.

- The participant develops hypereosinophilia.
 - Participants with absolute eosinophil counts >1500 cells/ μ L and signs and/or symptoms of target organ involvement that is not consistent with UC and/or with the participant's UC and medical history will be discontinued from study drug in consultation with the medical monitor. Participants will undergo appropriate medical evaluation, which should take into account the participant's known UC and past medical history according to the participant's history and medical records, including previous imaging, biopsies and laboratory findings. Evaluation of target organ involvement will involve additional diagnostic tests as appropriate, including laboratory tests, imaging (for example, echocardiogram, chest x-ray, CT scan), and biopsies. New onset cardiac, pulmonary, and skin findings in the setting of peripheral eosinophilia will be considered as target organ involvement, unless attributable to other causes.
 - Asymptomatic participants with an absolute eosinophil count >5000 cells/ μ L should have a repeat measurement to confirm the count. If the count is confirmed, the participant will be permanently discontinued from study drug and undergo appropriate medical evaluation.
- The participant has an AE, SAE, or a clinically significant change in a laboratory value that, in the opinion of the investigator, merits the discontinuation of the study drug and appropriate measures being taken.

Hepatic event or liver test abnormality

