8.2.5. Laboratory Tests

[Appendix 2](#) lists the clinical laboratory tests to be performed, and the SoA specifies when samples are routinely collected for clinical laboratory tests. Samples for laboratory testing will be obtained in the event of anaphylaxis or generalized urticaria, as described in Section 8.3.6.1 and

[Appendix 2](#), Section 10.2.2. Additional tests may be performed at any time during the study, as determined necessary by the investigator or as required by local regulations.

All protocol-required laboratory assessments, as defined in [Appendix 2](#), must be conducted in accordance with the SoA, standard collection requirements, and laboratory manual.

If laboratory values from nonprotocol specified laboratory assessments performed at an investigator-designated local laboratory require a change in participant management or are considered clinically significant by the investigator (for example, SAE, AE, or dose modification), then report the information as an AE.

Reviewing and recording test results

The investigator must review the laboratory results, document this review, and report any clinically relevant changes occurring during the study as an AE. The laboratory results must be retained with source documents, unless a Source Document Agreement or comparable document cites an electronic location that accommodates the expected retention duration.

Repeat testing after clinically significant abnormal findings

All laboratory tests with values considered clinically significantly abnormal during participation in the study or within 8 weeks after the last dose of study intervention should be repeated until the values return to normal or baseline or are no longer considered clinically significant by the investigator or the medical monitor. If such values do not return to normal/baseline within a period of time judged reasonable by the investigator, the etiology should be identified and the sponsor notified.

Blinding of laboratory test results

Laboratory results that could unblind the study will not be reported to investigative sites or other blinded personnel.

Sample retention

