9.4.4. Safety Analyses

Safety analyses will include AEs, SAEs, AESIs, C-SSRS, QIDS-SR16, vital signs, ECGs, and laboratory analytes, using the Safety Population data descriptively summarized by treatment group. Categorical safety measures will be summarized with incidence rates. Continuous safety measures will be summarized as mean change by visit. Exposure to study intervention will be calculated for each participant and summarized by treatment group.

Adverse events will be coded according to MedDRA and summarized by system organ class, preferred term, severity, and relationship to the study intervention. A TEAE is defined as an event that first occurred or worsened in severity after baseline, with baseline defined as all pre-existing conditions recorded at Visit 1 and any AEs recorded before the first dose of study intervention (that is, during the interval between Visits 1 and 2, and recorded with the time of onset before the first dose of study intervention). The treatment period will be used as the postbaseline period for the analysis. For events that are gender specific, the denominator and computation of the percentage will include only participants from the given gender.

The number and percentage of participants who experienced TEAEs, TEAEs by maximum severity, deaths, SAEs, TEAEs related to study intervention, discontinuations from the treatment due to an AE, and AESIs will be summarized. Treatment-emergent adverse events (all, by

maximum severity), SAEs including deaths, and AEs that lead to treatment discontinuation will be summarized and analyzed by MedDRA SOC and preferred term.

Treatment-related TEAEs (TEAEs related to study intervention) are defined as events that are indicated by the investigator on the eCRF to be related to treatment.

Adverse events of special interest will be identified by a standardized MedDRA query (SMQ) or a Lilly-defined MedDRA preferred term listing.

Follow-up emergent AEs, SAEs including deaths, and AEs that lead to study discontinuation will be summarized. All AEs, including pre-existing conditions, will be listed by participant, visit, preferred term, treatment group, severity, and relationship to the treatment.

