10.1.9. Study and Site Start and Closure

The study start date is the date on which the clinical study is open for recruitment of participants.

The study or a study site will be discontinued if the sponsor or its designee judges it necessary for medical, safety, regulatory, or other reasons consistent with applicable laws, regulations, and GCP.

Closure of study sites

Study sites will be closed upon study completion. A study site is considered closed when all required documents and study supplies have been collected and a study-site closure visit has been performed.

The investigator may initiate study-site closure at any time, provided a reasonable cause exists and sufficient notice is given in advance of the intended termination.

Reasons for the early closure of a study site by the sponsor or investigator may include, but are not limited to,

- failure of the investigator to comply with the protocol, the requirements of the IRB/IEC or local health authorities, the sponsor's procedures, or GCP guidelines
- inadequate recruitment of participants by the investigator, and
- discontinuation of further study intervention development.

Study stopping rules

The IAC will convene to evaluate unblinded safety data if

- 5 or more participants experience TEAEs in the same SOC or 3 or more participants experience a TEAE of CRS, and
 - these TEAEs are judged as either serious or severe, and
 - these TEAEs are related to blinded study treatment.

Study enrollment and/or further dosing may be stopped, pending the decision of the IAC (Section 9.5 and Section 10.1.5). If the study is not stopped, the IAC will meet periodically. Details are provided in the IAC charter.

Interim analyses will be performed as described in Section 9.5. Details will be provided in the SAP. If the study is deemed futile, study enrollment and/or further dosing may be stopped.

If the study is prematurely terminated or suspended, the sponsor shall promptly inform the investigators, the IECs/IRBs, the regulatory authorities, and any contract research organizations used in the study of the reason for termination or suspension, as specified by the applicable regulatory requirements. The investigator shall promptly inform the participant and assure appropriate participant therapy and/or follow-up.

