10.2.2. Laboratory Tests to be Obtained at Time of a Systemic Hypersensitivity Event

[figure not shown]
Selected tests may be obtained in the event of anaphylaxis or systemic allergic/hypersensitivity reactions. The samples should be collected as close as possible to the onset of the event.

Hypersensitivity Tests^a

CCI	
LY concentration (PK)	N-methylhistamine
	Complements
	Cytokine panel

Abbreviation: LY = LY3471851; NMH = N-methylhistamine; PK = pharmacokinetics.

^a Assayed by Lilly-designated laboratory. Results will not be provided to the investigative sites.

10.3. Appendix 3: Adverse Events: Definitions and Procedures for Recording, Evaluating, Follow up and Reporting

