4.6.3.2. Systemic Hypersensitivity Reactions (including cytokine release syndrome)

A search will be performed using the current MedDRA version Standardised MedDRA Queries (SMQs) to search for relevant events, using the following queries:

- Anaphylactic reaction SMQ (20000021)
- Hypersensitivity SMQ (20000214)
- Angioedema SMQ (20000024)

Events that satisfy the queries will be listed, by temporal order within patient ID, and will include SOC, PT, SMQ event categorization including detail on the scope (narrow or broad), reported AE term, AE onset and end dates, severity, seriousness, outcome, etc.

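### No section clearly requires the cytokine sample for suspected cytokine release syndrome, and the SAP gives hypersensitivity/CRS a listing but not the by-arm AESI count the protocol promises

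*Protocol*

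**What the plan says.** **Status of the event.** Protocol 8.3.6 puts "systemic allergic/hypersensitivity reactions, including CRS" first among the adverse events of special interest (AESIs). Section 2.3 gives CRS as an example within the same class and notes that the Phase 1 reports were Grade 1.

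**Sampling.** The subheading in 8.3.6.1 names CRS. Its operative sentence begins "In the case of generalized urticaria or anaphylaxis, additional samples as described in" Appendix 2. Section 8.2.5 says the same: "Samples for laboratory testing will be obtained in the event of anaphylaxis or generalized urticaria". Section 10.2.2, where the cytokine panel is listed, reads "Selected tests may be obtained in the event of anaphylaxis or systemic allergic/hypersensitivity reactions". For a suspected CRS, 7.1.1 refers to "a cytokine panel from a blood sample obtained at the time of the event", qualified as something to have where possible.

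**Consequences.** Under 7.1.1 an event judged possibly or probably CRS leads to discontinuation of study drug. Under 10.1.9 the internal assessment committee (IAC) convenes if "3 or more participants experience a TEAE of CRS" and those events are serious or severe and related to blinded treatment.

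**Analysis.** Protocol 9.4.4 says the number and percentage of participants with several outcomes, ending with "discontinuations from the treatment due to an AE, and AESIs will be summarized". SAP 4.6.3.2, whose title includes CRS, searches three standardised MedDRA queries (anaphylactic reaction, hypersensitivity, angioedema) and then says "Events that satisfy the queries will be listed, by temporal order within patient ID". It plans no count. SAP Section 1 states that the protocol's analyses are unchanged.

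**The concern.** There are two linked gaps.

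First, a site that follows the mandatory wording in 8.2.5 and 8.3.6.1 has no instruction to draw the Appendix 2 samples for a suspected CRS that presents without urticaria or anaphylaxis. Section 10.2.2 wants samples as close to onset as possible, so one missed because the wording was ambiguous may not be recoverable. The medical monitor would then make the 7.1.1 judgement without an input that section hopes to have.

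Second, a programmer who follows SAP 4.6.3.2 produces no by-arm summary for the AESI the protocol lists first, and has no stated way to identify CRS. The study is meant to inform dose selection, and Protocol 4.1 has Stage 1 interim analyses cover safety and dosing tolerability. A by-dose count for this class is therefore among the results a reader of the report will look for.

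**Working it through.** No power, alpha or sample-size figure is involved, so the check is a comparison of texts plus one small piece of arithmetic.

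**Sampling triggers, section by section**

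- *Protocol 2.3:* systemic hypersensitivity reactions, with CRS as an example. Further testing is stated as a consequence; the tests are not named.
- *8.3.6.1, subheading:* CRS included.
- *8.3.6.1, rule:* generalized urticaria or anaphylaxis only. Appendix 2 samples should be collected.
- *8.2.5:* the same two events. Samples will be obtained.
- *10.2.2:* anaphylaxis or systemic allergic/hypersensitivity reactions. Selected tests, with the cytokine panel among those listed, may be obtained.
- *8.5:* all systemic allergic/hypersensitivity reactions. Additional blood will be obtained, for PK only. It cites 8.3.6.1, whose own trigger is narrower.
- *Schedule of Activities comments:* extra samples around the onset of hypersensitivity events, on the PK row and on one redacted row.
- *7.1.1:* CRS named directly. A cytokine panel is one input, where possible.

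Take a suspected CRS with neither urticaria nor anaphylaxis. Sections 8.2.5 and the 8.3.6.1 rule do not reach it. Section 10.2.2 reaches it through the AESI class but only permits testing. Section 8.5 requires a PK sample. Section 7.1.1 hopes for a panel. The cytokine sample is therefore allowed but not clearly required, and the subheading and rule of 8.3.6.1 do not match.

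**Analysis commitments, side by side**

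- *Protocol 9.4.4:* number and percentage with AESIs, identified by a standardised query or a sponsor-defined preferred-term list.
- *SAP 4.6.2.1, overview table:* death, SAE, any TEAE, discontinuation due to an AE, severe TEAE. There is no AESI row.
- *SAP 4.6.3.2:* listing only; no query or preferred term named for CRS.
- *SAP 4.6.3.1, 4.6.3.3, 4.6.3.4 and 4.6.4:* counts for infections, malignancies, gastrointestinal perforations and injection site reactions. Malignancies and perforations are not on the AESI list in Protocol 8.3.6, yet they get counts.
- *SAP 4.6.2.1, general tables:* all TEAEs, and AEs leading to discontinuation, by preferred term and treatment group.

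**What the general tables capture.** Protocol 9.2 assumes about 40 to 80 participants per active arm and about 40 on placebo. One event is 1/80 = 1.25% to 1/40 = 2.5% of an arm. Both exceed the SAP's 1% threshold for a common TEAE, so a single TEAE coded to a CRS preferred term would also enter the common-TEAE and maximum-severity tables.

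**What they do not capture.** Systemic hypersensitivity spans many preferred terms, and a participant can contribute to several, so the rows cannot be added to give participants with any such reaction. An event judged possibly CRS under 7.1.1 but still recorded under its symptoms appears in no CRS row.

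**The case against.** The strongest reply has four parts.

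1. *The panel in 7.1.1 is supportive.* The judgement rests first on signs, symptoms, severity and timing relative to dosing. The IAC trigger in 10.1.9 requires no sample either. This stands. A reader might infer that CRS cases are left without any confirming sample, and the documents do not support that: 7.1.1 foresees a panel, 10.2.2 permits one, 8.5 requires PK blood, and 8.2.5 allows additional tests at any time.

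2. *CRS is already counted by arm.* This stands for events coded to a CRS term, through the TEAE and discontinuation tables, and through the SAE table if serious. A reader might infer that the report would give no CRS information by dose; that goes too far. It does not supply a class-level participant count or a count under the study's own CRS judgement. Protocol Appendix 3 asks for a diagnosis rather than symptoms whenever possible, which reduces the symptom-coding gap but does not close it.

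3. *The tests are already planned.* Protocol 9.4.4 and SAP 4.6 apply Fisher's exact test to categorical safety data, and SAP 4.6 names AESIs among the safety analyses. This stands, so no new method is needed. But SAP 4.6.3.2 defines no CRS variable for the test to act on.

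4. *Stage 2 dose decisions use the IAC's unblinded review, not this listing.* This also stands. The gap is in the planned report and is not shown to impair the IAC.

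**Conclusion.** The point holds as an inconsistency to be reconciled and a promised summary to be restored. The protocol sends sites different messages on whether suspected CRS calls for the cytokine sample, and the mandatory wording leaves it out. SAP 4.6.3.2 falls short of Protocol 9.4.4 although the SAP says nothing has changed.

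The consequence is confined to safety. The primary analysis, power and error rates are untouched. What can be lost is a time-critical sample in an uncommon event, and a by-arm count for a class of events in arms of about 40 to 80, where a few cases could change how the doses compare.

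Two assumptions matter. Redacted rows in 10.2.2 and the Schedule of Activities are not counted as omissions. Whether the three queries already retrieve a CRS preferred term cannot be settled from the documents, which is itself a reason for the SAP to name the term. The change should be made, but the plan is not unsound without it.

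**What to change.** **Protocol.** Reconcile 2.3, 7.1.1, 8.2.5, 8.3.6.1, 8.5 and 10.2.2 so that one trigger states whether suspected CRS is included and which samples it covers. Which rule to adopt is a clinical decision for the sponsor, and none is proposed here.

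**SAP 4.6.3.2.** Keep the listing. State how CRS events are identified: the preferred term or terms used, and whether the investigator and medical monitor judgement under 7.1.1 also counts. Add number and percentage by treatment group for participants with any systemic hypersensitivity reaction and, on a separate line, for CRS. Apply the Fisher's exact test already planned for categorical safety data.

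**Cost.** Minor wording changes in the protocol and one extra safety table. If the sponsor decides that suspected CRS is included, there would also be an occasional extra blood sample.
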